12.8.3 Request for Waiver of Consent for Screening Activities

Prior to the subject signing the consent for this study pre-screening activities listed in section [2.2.1](#) may be performed.

We request a waiver of consent for these activities as they involve only minimal risk to the subjects. A waiver will not adversely affect the rights and welfare of the subjects given that the activities are only intended to determine suitability for screening for participation in research protocols. These activities could not practicably be carried out without the waiver as central recruiting services, utilized in the NIH

Clinical Center, perform pre-screening activities for multiple studies and obtaining consent for each one is beyond their resources. The subjects will be provided with additional pertinent information after participation as they will be informed whether or not they are eligible to sign a consent for additional screening.

13 REGULATORY AND OPERATIONAL CONSIDERATIONS

13.1 STUDY DISCONTINUATION AND CLOSURE

This study may be temporarily suspended or prematurely terminated if there is sufficient reasonable cause. Written notification, documenting the reason for study suspension or termination, will be provided by the suspending or terminating party to study participants, investigator, funding agency, the Investigational New Drug (IND) sponsor and regulatory authorities. If the study is prematurely terminated or suspended, the Principal Investigator (PI) will promptly inform study participants, the Institutional Review Board (IRB), and sponsor and will provide the reason(s) for the termination or suspension. Study participants will be contacted, as applicable, and be informed of changes to study visit schedule.

Circumstances that may warrant termination or suspension include, but are not limited to:

- Determination of unexpected, significant, or unacceptable risk to participants
- Demonstration of efficacy that would warrant stopping
- Insufficient compliance to protocol requirements
- Data that are not sufficiently complete and/or evaluable
- Determination that the primary endpoint has been met
- Determination of futility

Study may resume once concerns about safety, protocol compliance, and data quality are addressed, and satisfy the sponsor, IRB and as applicable, Food and Drug Administration (FDA).

13.2 QUALITY ASSURANCE AND QUALITY CONTROL

The clinical site will perform internal quality management of study conduct, data and biological specimen collection, documentation and completion. An individualized quality management plan will be developed to describe a site's quality management.

Quality control (QC) procedures will be implemented beginning with the data entry system and data QC checks that will be run on the database will be generated. Any missing data or data anomalies will be communicated to the site(s) for clarification/resolution.

Following written Standard Operating Procedures (SOPs), the monitors will verify that the clinical trial is conducted and data are generated and biological specimens are collected, documented (recorded), and reported in compliance with the protocol, International Conference on Harmonisation Good Clinical Practice (ICH GCP), and applicable regulatory requirements (e.g., Good Laboratory Practices (GLP), Good Manufacturing Practices (GMP)).

The investigational site will provide direct access to all trial related sites, source data/documents, and reports for the purpose of monitoring and auditing by the sponsor, and inspection by local and regulatory authorities.

13.3 CONFLICT OF INTEREST POLICY

The independence of this study from any actual or perceived influence, such as by the pharmaceutical industry, is critical. Therefore, any actual conflict of interest of persons who have a role in the design, conduct, analysis, publication, or any aspect of this trial will be disclosed and managed. Furthermore, persons who have a perceived conflict of interest will be required to have such conflicts managed in a way that is appropriate to their participation in the design and conduct of this trial. The study leadership in conjunction with the NCI has established policies and procedures for all study group members to disclose all conflicts of interest and will establish a mechanism for the management of all reported dualities of interest.

13.4 CONFIDENTIALITY AND PRIVACY

Participant confidentiality and privacy is strictly held in trust by the participating investigators, their staff, and the sponsor(s). This confidentiality is extended to cover testing of biological samples and genetic tests in addition to the clinical information relating to participants. Therefore, the study protocol, documentation, data, and all other information generated will be held in strict confidence. No information concerning the study or the data will be released to any unauthorized third party without prior written approval of the sponsor.

All research activities will be conducted in as private a setting as possible.

The study monitor, other authorized representatives of the sponsor, representatives of the Institutional Review Board (IRB), and/or regulatory agencies may inspect all documents and records required to be maintained by the investigator, including but not limited to, medical records (office, clinic, or hospital) and pharmacy records for the participants in this study. The clinical study site will permit access to such records.

The study participant's contact information will be securely stored at each clinical site for internal use during the study. At the end of the study, all records will continue to be kept in a secure location for as long a period as dictated by the reviewing IRB, Institutional policies, or sponsor requirements.

Study participant research data, which is for purposes of statistical analysis and scientific reporting, will be transmitted to and stored. This will not include the participant's contact or identifying information. Rather, individual participants and their research data will be identified by a unique study identification number. The study data entry and study management systems used by research staff will be secured and password protected. At the end of the study, all study databases will be de-identified and archived by the IC.

To further protect the privacy of study participants, a Certificate of Confidentiality has been issued by the National Institutes of Health (NIH). This certificate protects identifiable research information from forced disclosure. It allows the investigator and others who have access to research records to refuse to disclose identifying information on research participation in any civil, criminal, administrative, legislative, or other proceeding, whether at the federal, state, or local level. By protecting researchers and institutions from being compelled to disclose information that would identify research participants, Certificates of Confidentiality help achieve the research objectives and promote participation in studies by helping assure confidentiality and privacy to participants.

14 PHARMACEUTICAL INFORMATION

14.1 MARIZOMIB (IND 139633)

14.1.1 Source

Marizomib is an investigational drug. The Center for Cancer Research (CCR), National Cancer Institute (NCI) will Sponsor the IND for this study. Marizomib will be supplied by the manufacturer (Celgene).

14.1.2 Human Toxicity

Refer to investigator brochure for detailed toxicity information.

14.1.3 Formulation and preparation

Marizomib Lyophile and Marizomib Lyophile Diluent are supplied in 2 vials as a kit placed in a single box that should be stored at 2°C to 8°C. Marizomib Lyophile and Marizomib Diluent are each provided in a 20-cc clear Type I glass vial with a Fluro-Tec[®] stopper and a Flip-off lid.

Marizomib Lyophile is supplied as a white to off white cake or powder of 2 mg marizomib and 60 mg sucrose per vial. Marizomib Lyophile Diluent is provided as a clear solution (20 mL) comprising 55% propylene glycol, 5% ethanol, and 40% citrate buffer (10 mM, pH 5).

Marizomib Lyophile vials are designated for single use only. For each subject treatment, 1 kit containing 1 vial of Marizomib Lyophile and 1 vial of Marizomib Diluent should be removed from the refrigerator. Do not warm the vials above 8°C.

The parenteral dosing solution of marizomib drug product from the lyophile formulation is prepared by removing 10 mL of Marizomib Diluent and adding it to the Marizomib Lyophile vial. (Note: Lyophile vials are sealed under vacuum and may pull syringed Diluent into the vial after needle insertion). Reconstitution should be performed under controlled, aseptic conditions. This results in a marizomib concentration of 0.2 mg/mL (2.0 mg in 10 mL/vial). The resulting reconstituted solution should be thoroughly mixed by vigorous shaking.

14.1.4 Stability and Storage

Marizomib Lyophile and Marizomib Diluent vials should be stored at 2°C to 8°C. The reconstituted marizomib solution should be thoroughly mixed by vigorous shaking and stored at 2°C to 8°C; the product should not be further diluted. The reconstituted MRZ dosing solution is stable in the dosing syringe for up to 2 hours in refrigerated conditions (2-8°C), AND up to an additional 1 hour when stored at Room Temperature (RT) conditions (20-25°C). A dosing syringe containing MRZ dosing solution removed from refrigeration and placed on an ambient surface will reach Room Temperature in approximately 10-15 minutes.

14.1.5 Administration procedures

Marizomib should be given as an intravenous infusion at 0.8 mg/m² over at least 10 minutes (+10 minutes)..

14.1.6 Incompatibilities

Marizomib is a second-generation irreversible proteasome inhibitor with a bicyclic β-lactone γ-lactam structure as below. Marizomib's lipophilic structure allows it to cross the blood-brain-barrier [16]. It inhibits the 20S proteasome, activates caspases and builds up reactive oxygen species to induce apoptosis in tumor cells [16].

Abbreviated Title: Ph II EP Marizomib

Version Date: 11/02/2020

14.1.7 Chemical name and structure:

(1R,4R,5S)-4-(2-chloroethyl)-1-((1S)-cyclohex-2-enyl(hydroxyl)methyl)-5-methyl-6-oxa-2-azabicyclo[3.2.0]heptane-3,7-dione

Formerly known as: 6-Oxa-2-azabicyclo[3.2.0]heptane-3,7-dione, 4-(2-chloroethyl)-1-[(S)-[(1S)-2-cyclohexen-1-yl]hydroxymethyl]-5-methyl-, (1R,4R,5S)

CAS Registry Number: 437742-34-2

Chemical class: Bicyclic γ -lactam β -lactone

Other chemical identifier: Salinosporamide A

Generic name: Marizomib

Trade name: Not assigned

Abbreviated name: NPI-0052, MRZ

Molecular formula: C₁₅H₂₀ClNO₄

[figure not shown]
Molecular weight: 313.78

Physical description: White crystalline solid

Pharmacological class: Proteasome inhibitor

Solubility in Organic solvents: Isopropanol (5 mg/mL), ethanol (10 mg/mL), methanol (17 mg/mL), acetonitrile (13 mg/mL), propylene glycol (6 mg/mL), tert-butanol (2 mg/mL)

Solubility in Aqueous buffer: 5.5 μ g/mL, pH 5

Chemical structure:

(Source: Ma, L and Diao, A et al. Anticancer Agents Med Chem. 2014 [18])

Abbreviated Title: *Ph II EP Marizomib*
Version Date: 11/02/2020

Marizomib appears to have a very low potential for drug: drug interactions as it is neither an inhibitor nor an inducer of hepatic CYPs from different species, it is not influenced by multiple drug resistant/ATP-binding cassette transporters and is inactive in a broad array of enzyme, ion channel, second messenger, and receptor assays.

16 APPENDICES

16.1 APPENDIX A: KARNOFSKY PERFORMANCE STATUS AND NEUROLOGICAL FUNCTION

Patient's performance status and Neurologic Functions will be graded according to the following scales:

Karnofsky Performance Scale	
Percent	Description
100	Normal, no complaints, no evidence of disease.
90	Able to carry on normal activity; minor signs or symptoms of disease.
80	Normal activity with effort; some signs or symptoms of disease.
70	Cares for self, unable to carry on normal activity or to do active work.
60	Requires occasional assistance, but is able to care for most of his/her needs.
50	Requires considerable assistance and frequent medical care.
40	Disabled, requires special care and assistance.
30	Severely disabled, hospitalization indicated. Death not imminent.
20	Very sick, hospitalization indicated. Death not imminent.
10	Moribund, fatal processes progressing rapidly.
0	Dead.

Neurologic Function	
+2	Definitely Better
+1	Possibly Better
0	Unchanged
-1	Possibly Worse
-2	Definitely Worse
B	Baseline

Neurologic Function Score

This method of neurologic evaluation notes the presence or absence of neurologic symptoms. This examination should coincide with objective measurement in tumor size.

- 0 No neurologic symptoms
- 1 Minor neurologic symptoms
- 2 Moderate neurologic symptoms – fully active
- 3 Moderate neurologic symptoms – less than fully active
- 4 Severe neurologic symptoms

16.2 APPENDIX B: MRI ACQUISITION PROTOCOL

Acquisition protocol

• Auto-align scout	(2 min)
• Pre-contrast T1	(2 min)
• High resolution T2 Volume	(5 min)
• FLAIR	(3 min)
• BOLD/ASL (optional)	(14 min)
• Pre-contrast variable flip angle T1 maps	(1 min)
• Permeability (T1 dynamic)	(6 min)
• Post-contrast variable flip angle T1 maps	(1 min)
• Diffusion Tensor Imaging	(7 min)
• Perfusion (T2/T2*)	(3 min)
• 3D Post-contrast	(5 min)
• Post-contrast T1	(2 min)

Our proposed acquisition protocol is described in the box, and consists of approximately 65 minutes of imaging time (typically 90 to 120 minutes of time that the subject is in the magnet, counting setup and scan delays). Each of these datasets will be analyzed using tools that are published and well known in the neuroradiologic community. A brief outline of our analysis techniques follows:

Dynamic Contrast Enhanced – Magnetic Resonance Imaging (DCE-MRI)

DCE-MRI will be used to monitor the effects on tumor vasculature through parameters reflecting both tumor perfusion and permeability. This sequence uses a bolus injection of 0.1 mmol/kg of Gd-DTPA. Data will be analyzed using the standard Tofts/Kermode model with the typical approach of Patlak et al [21].

T2-weighted contrast-enhanced MRI or perfusion weighted imaging (PWI)

A second dose of Gd-DTPA (typically 0.1-0.2 mmol/kg) is administered for first-pass T2/T2-weighted imaging. We use a combination gradient-echo/spin echo approach to allow estimation of tumor vascular size based on the equations in the box. As shown in our earlier work [22], this can be used to estimate average vessel diameter, which we believe may change with effective anti-angiogenic therapy. This approach also provides estimates of cerebral blood volume (CBV), cerebral blood flow (CBF), mean transit time (MTT), and perfusion efficiency (1/MTT).

Diffusion Tensor Imaging (DTI)

We will measure the full water self-diffusion tensor before and after treatment in this patient population. The tensor fractional anisotropy (FA) will be calculated and can be used to define white matter tract directions and tumor invasion. Apparent diffusion coefficient (ADC) maps will also be calculated.

Simultaneous Blood Oxygenation Level Dependent (BOLD) and Arterial Spin Labeling (ASL) Imaging (Optional)

Combined BOLD/ASL imaging is a non-contrast approach to simultaneously measuring cerebral blood flow (ASL) and cerebral metabolic rate of oxygen consumption (BOLD) [31].

Our standard approach for this is to use a pulsed ASL sequence followed by a single-shot, gradient echo (GE) echo planar imaging acquisition. Two echoes are acquired, short echo (TE = 11 ms) for ASL (CBF maps) and longer echo (TE = 40 ms) for BOLD. Patients are administered room air and 100% oxygen at varying time points throughout the scan. The gas paradigm is as follows: baseline room air (8 min) – 100% O₂ (4 min) – washout room air (2 min) at a constant ~35 L/min flow rate. Blood oxygen levels are continuously monitored throughout the scan with a pulse oximeter.

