2.2.2 Screening activities performed after a consent for screening has been signed

The following activities will be performed only after the subject has signed the consent for this study for screening. Assessments performed at outside facilities or on another NIH protocol (01-C-0129 CCR Screening protocol or 16-C-0151 NOB Natural History Protocol) within the timelines below may also be used to determine eligibility once a patient has signed the consent. The screening evaluation must be completed within 14 timelines noted in Section [2.4](#) unless otherwise noted:

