2.2.2.1 Imaging

- MRI head and/or spine with gadolinium to confirm progressive disease. MRI parameters should follow the specifications detailed in [Appendix B](#). If the steroid dose is increased between the date of imaging and consent, a new screening MRI is required after patient has been on a stable steroid dose for at least 5 days.
- Patients with prior therapy that included interstitial brachytherapy or stereotactic radiosurgery must have confirmation of true progressive disease rather than radiation necrosis based upon either PET or Thallium scanning, MR spectroscopy, or surgical/pathological documentation of recurrent disease (Screening only).

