2.4 BASELINE EVALUATION

Tests done at screening do not need to be repeated at baseline if performed in designated time frame prior to start of study drug.

Within 14 days prior to first dose:

- MRI of the head and/or spine with gadolinium as specified in [Appendix B](#).
- Archived tumor samples will be collected to do molecular studies as described in Section [5.3](#). If the patient has previously been on another study at NIH, and the required molecular profiling has been done, then additional pathology material may not be needed (any time prior to treatment initiation).
- The MDASI-BT and/or MDASI-SP . The choice of instrument will be based on the location of the index lesion for study enrollment. This may be in the brain (MDASI-BT), spine (MDASI-SP) or both (completing both instruments if lesions in the brain and spine are being followed for response). (For English speaking subjects only).
- Research blood for SNP Studies (See section [5.1.2](#))
- Research blood for Pharmacogenomic Studies (Cohort 1 only) (See section [5.1.2](#))
- Concomitant Medications
- Adverse events
- EKG (within 3 days prior to first dose)
- Subjects will complete and sign an NIH advanced directives form which is mandatory on this study.

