⁸ MRI head and/or spine with gadolinium at screening/baseline and every 8 weeks after beginning of treatment. Confirmatory scans should also be obtained in 4-8 weeks period of time following initial documentation of objective response. Patients with prior therapy that included interstitial brachytherapy or stereotactic radiosurgery must have confirmation of true progressive disease at screening rather than radiation necrosis based upon either PET or Thallium scanning, MR spectroscopy, or surgical/pathological documentation of recurrent disease. After initial confirmation of progressive disease at screening, these patients will be evaluated during treatment with regular MRI.

⁹ At baseline and then within 14 days prior to each imaging study.

¹⁰ All SAEs ongoing at the 28-Day Safety Follow-up visit must be monitored and followed up by the Investigator until stabilization or until the outcome is known, unless the subject is documented as “lost to follow-up.” Subjects with PD after the 28-Day Safety Follow-up visit, will be followed every 6 months (± 1 month) for survival (including assessment of any further anticancer therapy) by phone call or e-mail.

Subjects without PD at the 28-Day Safety Follow-up visit should continue follow up visits and tumor imaging by MRI per schedule in the Section **3.5.2**

¹¹ If subjects are unable or not willing to come to NIH to for follow up visits, they will be followed by phone call or e-mail for survival, adverse events (for 1 year only) and further tumor therapy.

¹² If significant (> 3 kg) weight loss or gain is observed during a cycle.

¹³ Within 2 hours after study drug infusion and additionally any time if clinically indicated.

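### Appendix B includes a perfusion sequence with a second gadolinium dose, not marked optional, whose outputs serve no objective, endpoint, response criterion or Section 10 analysis

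*Combined protocol and SAP*

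**What the plan says.** Appendix B (section 16.2) sets out the MRI acquisition. Of the permeability sequence it says: "This sequence uses a bolus injection of 0.1 mmol/kg of Gd-DTPA". Of the perfusion sequence it says: "A second dose of Gd-DTPA (typically 0.1-0.2 mmol/kg) is administered for first-pass" imaging. Only the combined BOLD/ASL acquisition, which uses no contrast, is marked optional. Perfusion is to yield an estimate of vessel diameter, which the authors say "we believe may change with effective anti-angiogenic therapy", together with blood volume, blood flow, transit time and the inverse of transit time.

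Two sections bring Appendix B into the trial. Section 2.2.2.1 says "MRI parameters should follow the specifications detailed in" the appendix, and section 2.4 asks for "MRI of the head and/or spine with gadolinium as specified in" it. Section 2.2.2 leaves some room: "Assessments performed at outside facilities or on another NIH protocol" may be used for eligibility if they fall within the time limits. Footnote 8 of the study calendar (section 3.6) schedules "MRI head and/or spine with gadolinium at screening/baseline and every 8 weeks after beginning of treatment" without citing Appendix B. Section 6.3.2 asks for one method and one technique for each lesion at baseline and follow-up.

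On safety, section 12.6.2 lists possible kidney damage from gadolinium-enhanced MRI. Section 2.1.1.7 requires creatinine no higher than 1.5 times the institutional upper limit, or an eGFR of at least 60.

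**The concern.** A patient scanned as Appendix B describes receives a second contrast injection for measurements that answer no question the trial asks. The one sequence marked optional needs no contrast, while the one needing a further injection is not optional. The reason given for measuring vessel size concerns anti-angiogenic treatment. The protocol presents marizomib as a proteasome inhibitor acting on the NF-κB pathway, and no objective concerns angiogenesis.

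What is at stake is patient burden and contrast exposure, not the validity of the primary result.

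**Working it through.** The plan states no total contrast dose, so there is no figure to reproduce. The check is a trace of the perfusion outputs through the plan, followed by simple arithmetic.

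**1. Where the perfusion outputs could be used**

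| Place | What it contains | Perfusion output used? |
|---|---|---|
| Section 1.1, objectives | PFS, OS, response, safety, patient-reported symptoms, *RELA* fusion, gene panel, NF-κB expression, germline variants | No |
| Section 2.2.2.1, necrosis work-up | PET, thallium, MR spectroscopy, pathology | No |
| Section 5.1, correlative studies | Tissue and blood only | No |
| Sections 6.3 to 6.3.7 and Table 6 | T1 enhancement, T2/FLAIR, new lesions, steroids, clinical status | No |
| Sections 10.1.1 and 10.1.2, endpoints | PFS6, PFS12, PFS, OS, response, safety, symptoms | No |
| Section 10.4, analyses | Survival, symptom, safety and genomic analyses | No |
| Appendix B | States that each dataset will be analysed and outlines how the maps are derived | Image processing only |

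**2. Contrast per Appendix B scan** (doses from Appendix B)

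- Permeability bolus: 0.1 mmol/kg.
- Perfusion dose: 0.1 to 0.2 mmol/kg.
- Total: 0.1 + 0.1 = 0.2 to 0.1 + 0.2 = 0.3 mmol/kg.
- Ratio to the first dose alone: 0.2 / 0.1 = 2 to 0.3 / 0.1 = 3.

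**3. Extra contrast per patient, by reading of the plan**

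- A qualifying outside scan without perfusion is accepted and no later scan uses it: 0.
- One screening/baseline scan under Appendix B: 1 × (0.1 to 0.2) = 0.1 to 0.2 mmol/kg. A repeat screening MRI after a steroid increase (section 2.2.2.1) could add one more.
- Illustration only, assuming that Appendix B applies to every 8-weekly scan and the patient completes all 24 cycles: 24 × 4 = 96 weeks; 96 / 8 = 12 scans; 12 + 1 baseline = 13; 13 × (0.1 to 0.2) = 1.3 to 2.6 mmol/kg. Confirmatory, 28-day and long-term follow-up scans are not counted, so this is not a ceiling.

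**4. Scan time** (minutes as listed in Appendix B)

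- All sequences: 2 + 2 + 5 + 3 + 14 + 1 + 6 + 1 + 7 + 3 + 5 + 2 = 51.
- Without optional BOLD/ASL: 51 − 14 = 37.
- Without perfusion as well: 37 − 3 = 34.

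The text gives about 65 minutes. The list as extracted may be incomplete, and nothing here depends on the difference.

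**The case against.** **The data are to be analysed.** Appendix B does say that each dataset will be analysed, so a reader who infers that no analysis of any kind is planned goes too far. The statement covers image processing and links to no objective or outcome. The gap is in Section 10, not in the appendix.

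**Renal safeguards exist.** This is fair. Section 2.1.1.7 limits renal impairment, and creatinine is in the screening and pre-dose laboratory panels. These limits reduce the risk without removing it: the screening MRI may precede the laboratory results, and because the two renal limits are joined by an *or*, a patient with an eGFR below 60 might still qualify.

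**The wording is soft.** The screening instruction is a *should*, the acquisition protocol is called proposed, the second dose is given as typical, and outside scans are accepted. This lowers the bottom of the range to zero. It does not make the sequence optional, and the baseline instruction in section 2.4 is firmer.

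**The same-technique rule already keeps contrast conditions constant.** This is partly right, and it bears on the remedy. If perfusion were made optional with nothing else changed, and if the list in Appendix B is the acquisition order, the T1 image read for Table 6 could follow 0.1 mmol/kg at one visit and 0.2 to 0.3 at another. The change must therefore include the order of acquisition.

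**Perfusion is singled out.** Permeability and diffusion imaging also serve no objective. Perfusion differs in being the only sequence described as needing a further injection.

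**Conclusion.** The mismatch is clear from the text: a second contrast dose, not marked optional, supports measurements that no objective, endpoint, response criterion or Section 10 analysis uses. Its size is 0.2 to 0.3 rather than 0.1 mmol/kg per Appendix B scan. Confidence is high on the mismatch and low on the harm and on total exposure.

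Three stronger readings are not supported:

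- **Material renal harm.** The documents name the risk without a rate and restrict renal impairment at entry. The harm is taken to be small and cannot be estimated.
- **A second dose at every scan.** Appendix B is cited only for screening and baseline. Section 6.3.2 may extend it to on-treatment scans, but that is an inference. Whether spine-only patients receive the sequence is not stated either.
- **A distorted response or PFS6 reading.** Perfusion is listed before the 3D post-contrast and post-contrast T1 images, but the appendix does not say that the list is the acquisition order, and no effect on the reading is shown. The order matters only as a condition of making perfusion optional. The decision rules and sample size are untouched.

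This is a cheap improvement for the sponsor to consider.

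**What to change.** Amend Appendix B in three places, adopted together:

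1. Mark the perfusion (T2/T2*) sequence and its second injection optional, as BOLD/ASL already is.
2. Require the 3D post-contrast and post-contrast T1 images to be acquired before any perfusion injection. The T1 image used for Table 6 then follows the 0.1 mmol/kg dose whether or not perfusion is done, which keeps to the same-technique rule in section 6.3.2.
3. State that perfusion at one scan does not require it at later scans.

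The cost is one word, one sentence and a reordered list. Reordering adds no listed scan time, and leaving perfusion out saves 3 of the 37 non-optional minutes. The loss is some exploratory perfusion and vessel-size data, and series that may be incomplete within a patient. If the sponsor wants those data, the alternative is to add an exploratory objective and a matching analysis in section 10.4.5, which would give the second injection a stated purpose.
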